10.5. Protocol Violations

Serious protocol deviations such as discontinuation of experimental treatment unrelated to adverse events (AEs) will be carefully recorded and regularly reviewed by co-Principal Investigators. Remedial changes in procedure will be recommended where feasible to reduce the incidence of such deviations. The causes and circumstances of all violations will be documented where known for purposes of future secondary analyses and interpretation. Because all primary analyses will be intent-to-treat, it is essential that violations be kept to a minimum, especially where it is possible to influence their rate of occurrence. A missed study visit will not be considered a protocol violation unless the study drug was scheduled to be dispensed at the visit, the subject did not have necessary labs done, or the subject has not been stable.

10.6. Safety Analysis

All patients will be assessed for toxicity and included in the safety analysis. This analysis will include summaries of the incidence and grade of toxicities. Safety interim analyses will be performed at days 14, 30, 60, 90, 118, and 184, and will be reported at each DSMB meeting. SAEs will be evaluated by the DSMB..

11 CHAPTER 8: QUALITY CONTROL AND DATA HANDLING

11.1. Personnel Training

Prior to enrolling the first subject in the study protocol, the Principal Investigators will ensure that the Investigator staff has completed appropriate training and that all documentation including IRB approval is completed and available. The purpose of training is to ensure that study personnel are carrying out the protocol in a consistent way and adhering to good clinical practice guidelines. Staff will have current Human Subjects

Training Certification on file. Before enrollment begins, study staff who will perform the outcome assessments will be trained in all procedures, including completion of the REDCap database.

The co-PIs and research staff will constitute the first line of monitoring of the safety of the human participants. Surveillance for AEs will consist of questioning subjects about potential AEs at every study contact, having subjects report any AE to the study team, and having subjects undergo vital sign checks and physical exams during each study visit. Laboratories will be performed at selected visits and checked.

All study personnel are required to read the consent form, the protocol, and the IB.

11.2. Data Quality

The co-PIs and research staff will perform continuous monitoring of data quality and completion of CRFs. All consent forms and screening logs will be subject to audit by the University of Pennsylvania. Summary statistics from the screening logs will be sent to Merck quarterly or as requested. Finally, Merck staff reviews the reporting, documentation and follow-up of SAEs to assure that these events were handled according to required study procedures. All data on AEs and SAEs will be made available to the DSMB, as per the timeline outlined in the DSMB Charter.

11.3. Audit and Inspection

Inspections may be carried out by regulatory health authority representatives [i.e., FDA] as well as the IRB.

11.4. Archiving

Essential documents shall be archived safely and securely in such a way that ensures that they are readily available upon authorities' request. Patient (hospital) files will be archived according to local regulations and in accordance with the maximum period of time permitted by the hospital, institution or private practice.

12 CHAPTER 9: PARTICIPANT SAFETY AND CONFIDENTIALITY

12.1. Informed Consent

Informed Consent will be obtained for enrollment from participants. For each consent process, study personnel will discuss the details of the study, the risks and benefits, and the subject's rights and responsibilities if they choose to participate in the trial and their right to refuse to participate. It will be made clear that their clinical care will not be affected by their decision.

Each subject will have ample time and opportunity to ask questions and will be informed about the right to withdraw from the study at any time without any disadvantage and without having to provide reasons for this decision.

Only after the subject consents voluntarily and agrees to sign the ICF and has done so, may he/she enter the study. Additionally, the investigator and other information provider (if any) will sign and date the form. The subject will receive a copy of the signed and dated form.

The signed informed consent statement is to remain in the investigator site file or

If the patient is not capable of providing a signature, a verbal statement of consent can also be given in the presence of an impartial witness (independent of the investigator). This is to be documented by a signature from the informing physician as well as by a signature from the witness.

The ICF and any other written information provided to subjects / legal representatives or proxy consenters will be revised whenever important new information becomes available that may be relevant to the subject's consent, or there is an amendment to the protocol that necessitates a change to the content of the subject information and / or the written ICF. The investigator will inform the subject / legal representative or proxy consenter of changes in a timely manner and will ask the subject to confirm his/her participation in the study by signing the revised ICF. Any revised written ICF and written information must receive the IEC/IRB's approval in advance of use.

12.2. Institutional Review Board Process

Study staff will obtain IRB approval before any study procedures are initiated.

12.3. Insurance

The heart transplant itself will be paid for by subjects' insurance carriers, and does not require any additional pre-authorization because of the potential to receive a heart from a hepatitis C-positive donor. The costs of all visits and tests described above will be billed to the insurance carrier, except for the blood draw for research purposes (which includes the hepatitis C genotype test, which is based on a laboratory-developed test using materials purchased from the commercial entity that developed this test, and will be paid for by the research team), and the study drug, which will be paid for by Merck. Subjects are still responsible for any deductibles or applicable co-pays for routine office visits, blood work and procedures. We do not expect subjects to have health insurance coverage/payment issues due to becoming infected with hepatitis C, per se, and the study is designed so subjects do not require additional study visits post-transplant, provided there are no adverse events.

12.4. Laboratory Values

The following clinical laboratory tests will be measured and repeated at time points specified in schedule of procedures (section 8.2.1) and as clinically indicated.

12.4.1. Chemistry

- Hepatic function panel including alanine aminotransferase, aspartate aminotransferase, alkaline phosphatase, total and direct bilirubin, and albumin.
- Basic metabolic panel including BUN and creatinine.

12.4.2. Serum virologic testing

- HCV RNA (with Genotyping per protocol)
- Hepatitis B surface antigen
- HIV antibody testing.
- HBV Core Antibody (as needed)

12.4.3. Pregnancy Testing

Blood and urine pregnancy tests will be performed (as appropriate) per the schedule of procedures (section 5.2).

12.4.4. Hepatitis C Viral Kinetics

Each time standard of care laboratories are drawn, subjects may have one additional purple -top tube drawn (4cc of blood). This blood test is optional. The research coordinator will process the tube and store it in a -80° freezer in the Perelman Center for Advanced Medicine 7th Floor Gastroenterology Research Office. Each month, these tubes will be shipped to Abbott Pharmaceuticals so they can test for HCV antibodies, HCV core antigen, and HCV RNA. These additional tests will be included in the informed consent process for all subjects. Abbott will perform these tests free of charge to University of Pennsylvania once both are able to reach a Material Transfer Agreement (MTA).

12.4.5. IL28B Genotype Testing

At the time of the subject's heart transplant, both donor and recipient will have one tube of blood drawn to be used for IL28B Genotype Testing. Donors' families will have already agreed to this test when they consent to research testing. Recipients must sign an additional consent form before this test is performed.

12.5. Zepatier Related Laboratory Abnormalities and Drug Interactions

Laboratory Abnormalities

The following laboratory abnormalities were observed in studies done with Zepatier:

Late elevations in aminotransferase levels greater than 5 times the upper limit of normal generally occurred in around 1-3% of patients in previous Zepatier clinical trials; these increases were rarely associated with hyperbilirubinemia. These abnormalities were reversible and had no major clinical consequences.

Effects of Zepatier on antiretrovirals:

- Atazanavir/ritonavir 300/100mg co-administered with MK-5172 200mg daily somewhat increased atazanavir exposure (AUC increased 43%, Cmax increased 12%, C24 increased 23%). Co-administration of these medications is not recommended.

- Darunivir/ritonavir 600/100 mg co-administered with MK-5172 200 mg was not significantly altered by either MK-5172 or MK-8742. However, due to DRV/r effects on Zepatier exposure, co-administration is not recommended.
- Efavirenz was not significantly impacted when co-administered with Zepatier, though it may negatively impact Zepatier exposure.
- Lopinavir/ritonavir exposures were not significantly impacted when co-administered with Zepatier. However, due to LPV/r effects on Zepatier exposure, co-administration is not recommended.

Effect of Antiretrovirals on Zepatier:

- Atazanavir/ritonavir 300/100mg co-administered with MK-5172 200mg significantly increased exposure of MK-5172 (AUC increased 10.58-fold, Cmax increased 6.24-fold, and C24 increased 11.6-fold). These findings were similar when ATV/r was combined with 50mg MK-8742. MK-8742 AUC geometric mean ratio (GMR) was 4.76, probably due to ATV/r CYP3A4/Pgp inhibition and possible inhibition of OATP-mediated disposition of MK-8742. Co-administration of these medications is not recommended.
- Exposures of MK-5172 were significantly increased when MK-5172 200 mg was co-administered with darunavir/ritonavir 600/100 mg daily. MK-5172 AUC increased 7.5-fold, Cmax increased 5.27-fold, and C24 increased 8-fold. MK-8742 exposures were also significantly increased when combined with DRV/r 600/100 mg daily. MK-8742 AUC GMR following co-administration was 1.66. This increase is likely caused by CYP3A4/Pgp inhibition by DRV/r and possibly inhibition of OATP-mediated disposition of MK-8742. For these reasons, co-administration of Zepatier and DVR/r is not recommended.
- Efavirenz 600mg co-administration with MK-5172 200 mg decreased MK-5172 AUC by 84%, most likely due to CYP3A4 induction. The same dose EFV combined with MK-5172 50 mg also decreased MK-8742 AUC 54% for the same reasons. Co-administration of these medications may cause sub-therapeutic MK-5172 exposure.
- Lopinavir/ritonavir 400/100 mg co-administered with MK-5172 200 mg significantly increased MK-5172 exposure. MK-5172 AUC increased 12.86-fold, Cmax increase 7.31-fold, and C24 increased 21.7-fold. When the same dose of LPV/r was administered with MK-8742 50 mg, MK-8742 AUC GMR was increased to 3.71. LPV/r likely impacts MK-8742 exposures due to CYP3A4/Pgp inhibition and possible inhibition of OATP-mediated disposition. Co-administration of these medications is not recommended.

Effect of Zepatier on Other Drugs:

- Rosuvastatin 10 mg co-administered with Zepatier 200/50 mg increased rosuvastatin exposure. Rosuvastatin AUC and Cmax were increased 59% and 325% respectively when exposed to MK-5172 alone and 126% and 449% when exposed to the combined Zepatier pill. The most likely cause of the increase is pre-systemic inhibition of rosuvastatin efflux in the liver and/or gut due to BCRP inhibition. Clinicians may want to avoid co-administration of Zepatier and rosuvastatin.
- Midazolam 2 mg/mL combined with multi-dose MK-5172 200 mg daily decreased midazolam AUC to 34%. MK-5172 is likely a weak CYP3A4 inhibitor.
- Multiple oral doses of rifampin did not significantly affect MK-5172 AUC, but reduced C24h by 85%. This decrease was presumably due to the combined effect of OATP inhibition and CYP3A4/Pgp induction by chronic rifampin administration. Clinicians should avoid co-administration of these medications until further data becomes available.

Effect of Other Drugs on Zepatier:

- Rosuvastatin 10 mg co-administered with Zepatier 200/50 mg did not significantly alter MK-5172/8742 exposure. However, due to Zepatier effects on rosuvastatin exposure, clinicians may wish to avoid co-administration.

- Ketoconazole (CYP3A4 and P-gp inhibitor) approximately tripled MK-5172 AUC. In healthy male subjects taking 400 mg multi-dose ketoconazole, MK-8742 AUC increased by 31%.
- Combining MK-5172 200 mg and a single dose of 600 mg IV rifampin caused a 12.6-fold increase in MK-5172 AUC, compared to an 8.35-fold increase with a single dose of oral rifampin 600 mg. This is likely due to P-gp and OATP inhibition by rifampin. Clinicians should avoid co-administration of these medications until further data becomes available.

12.6. Other Events

We will not discontinue study drug for clinical events not thought to be serious drug-related AEs. For example, a hospitalization for clinical worsening may or may not result in cessation of trial participation. Such events could result in missing data for primary and secondary endpoints, comprising the integrity of the analysis. This trial does prohibit certain therapies, thus there may be a reason to stop study drug participation under such circumstances. Even if subjects are withdrawn from the study drug, outcome assessments will continue, allowing analysis by intent-to-treat.

12.7. Safety and Adverse Events

12.7.1. Definitions

Adverse event (AE): Any untoward medical occurrence associated with the protocol procedures, whether or not considered product or process related. Any symptom, sign, illness or experience that develops or worsens in severity during the course of the study. Inter-current illnesses or injuries should be regarded as AEs. Abnormal results of diagnostic procedures are considered to be AEs if the abnormality:

- results in study withdrawal
- is associated with a serious AE
- is associated with clinical signs or symptoms
- leads to additional treatment or to further diagnostic tests
- is considered by the investigator to be of clinical significance

Serious adverse event (SAE): Adverse events are classified as serious or non-serious. A *serious adverse event* is any AE that is:

- fatal
- life-threatening
- requires or prolongs hospital stay
- results in persistent or significant disability or incapacity
- a congenital anomaly or birth defect
- an important medical event

Important medical events are those that may not be immediately life threatening, but are clearly of major clinical significance. They may jeopardize the subject, and may require intervention to prevent one of the other serious outcomes noted above. For example, drug overdose or abuse, a seizure that did not result in in-subject hospitalization or intensive treatment of bronchospasm in an emergency department would typically be considered serious.

All AEs that do not meet any of the criteria for serious should be regarded as *non-serious AEs*.

Suspected adverse reaction: Any adverse event for which there is a reasonable possibility that the drug/investigational product caused the adverse event. For reporting purposes, "reasonable possibility" means

there is evidence to suggest a causal relationship between the drug/investigational product and the adverse event.

Unanticipated Adverse Device Effect (ADE): is any serious adverse effect on health or safety, or any life-threatening problem or death caused by, or associated with, a device, if that effect, problem, or death was not previously identified in nature, severity, or degree of incidence in the investigational plan or application, or any other unanticipated serious problem associated with a device that relates to the rights, safety, or welfare of subjects.

12.7.2. Classifying Adverse Events

Severity

The intensity of the AE is classified according to the CTCAEv4.0.¹⁴ Grade refers to the severity (intensity) of the AE:

- **CTCAEv4 Grade 1:** mild; asymptomatic or mild symptoms; clinical or diagnostic observations only; intervention is not indicated.
- **CTCAEv4 Grade 2:** moderate; minimal, local, or noninvasive intervention is indicated; limiting to age-appropriate instrumental activities of daily living (ADL; instrumental ADL refers to preparing meals, shopping for groceries or clothes, using the telephone, managing money, etc).
- **CTCAEv4 Grade 3:** severe or medically significant but not immediately life threatening; hospitalization or prolongation of hospitalization is indicated; disabling; limiting to self-care ADL (self-care ADL refers to bathing, dressing and undressing, feeding self, using the toilet, taking medications, and not bedridden).
- **CTCAEv4 Grade 4:** life-threatening consequences; urgent intervention is indicated.
- **CTCAEv4 Grade 5:** death due to an AE.

Expectedness

AEs must be assessed as to whether they were expected to occur or were unexpected, meaning not anticipated based on current knowledge found in the protocol, investigator brochure, product insert, or label.

Expected: an AE/ADE known to be associated with the intervention or condition under study.

Unexpected: an AE/ADE for which the nature or severity is not consistent with information about the condition under study or intervention in the protocol, consent form, product brochure, or investigator brochure.

OHRP defines an **unexpected AE** as any AE occurring in one or more subjects participating in a research protocol, the nature, severity, or frequency of which is **not** consistent with either:

- 1) the known or foreseeable risk of AEs associated with the procedures involved in the research that are described in a) the protocol-related documents, such as the IRB-approved research protocol, any applicable investigator brochure, and the current IRB-approved informed consent document, and b) other relevant sources of information, such as product labeling and package inserts; or
- 2) the expected natural progression of any underlying disease, disorder, or condition of the subject(s) experiencing the AE and the subject's predisposing risk factor profile for the AE.

Relatedness

- 1) **Definite:** the AE/ADE is clearly related to the research procedures
- 2) **Probably:** the AE/ADE is likely related to the research procedures
- 3) **Possible:** the AE/ADE may be related to the research procedures
- 4) **Unlikely:** the AE/ADE is doubtfully related to the research procedures
- 5) **Unrelated:** the AE/ADE is clearly not related to the research procedures

For each identified AE/ADE, an entry on the AE/ADE form will be completed. Reporting procedures should be started immediately upon learning of a SAE/ADE.

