Number of subjects	Estimated 10 HCV-negative subjects transplanted with a heart from an HCV-positive donor
Plan for statistical analysis	
Primary endpoint:
 
 • Post-treatment sustained virologic response (SVR)

	
Secondary endpoints:
 
• Determine if there are major adverse events attributable to HCV therapy in post-heart transplant patients.• Evaluate 1-year heart graft survival in HCV-negative patients who receive a heart transplant from an HCV-positive donor• Determine the rates of spontaneous HCV clearance among HCV-negative patients with heart failure receiving a heart from an HCV-positive donor 
Data analysis:
 
The primary analysis will be based on a calculation of SVR rates (number of subjects with SVR-12; negative HCV RNA 12 weeks after completing Zepatier therapy) / (number of subjects treated with Zepatier post-heart transplantation)

--	---

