5.2. Specific aims

Primary aim:

1. Primary efficacy objective: To determine sustained virologic response (SVR) rates of open-label Zepatier in hepatitis C virus (HCV) negative patients who receive a heart transplant from a genotype 1 or 4 HCV-positive donor, leading to post-transplantation de-novo HCV infection.
2. Primary safety objective: To determine the safety of administration of open-label Zepatier among HCV-negative patients who receive a heart transplant from a genotype 1 or 4 HCV-positive donor and develop post-transplant HCV infection.

Secondary aim:

1. To determine 1-year graft survival rates of HCV-negative heart transplant patients who receive a heart transplant from a genotype 1 or 4 HCV-positive donor, including those who spontaneously clear HCV and those who receive open-label Zepatier upon development of de-novo HCV.
2. To obtain preliminary data on the distribution of changes in circulating biomarkers of endothelial damage and coronary vasculopathy in HCV-negative patients transplanted with hearts from HCV-positive donors prior to HCV treatment, after viral clearance, and after SVR.
3. To evaluate rates of spontaneous clearance of HCV among HCV-negative patients who receive a heart transplant from a genotype 1 or 4 HCV-positive donor.
4. To identify the viral reservoirs leading to HCV transmission in HCV-negative patients receiving a heart transplant from a HCV-positive donor based on endomyocardial biopsies, measures of HCV antigens in peripheral mononuclear blood cells, and histological examination of arterial and venous tissue surrounding the transplanted heart.
5. To compare the quality-of-life of HCV-negative patients receiving a heart transplant from a HCV-positive donor to those of similar patients remaining on the waitlist for a standard deceased donor heart transplant.

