9.2.1. Safety

Subject safety and adverse events will be based in CTCAE Version 4 criteria, listed in Section 13, and will include adverse events and serious adverse events, related both to receipt of a heart transplant from an HCV-positive donor among HCV-negative subjects with heart failure, and adverse events related to administration of Zepatier.

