12.7.3. Interpretation of Definitions

AE Reporting Period

The study period during which AEs must be reported is normally defined as the time of consent to the end of the study treatment follow-up. However, for this study, the AE reporting period will be divided based on the three phases of the study.

- a. **Screening phase:** When all screening tests have been done, we will assess for any AEs related to the screening tests at the time of communication with the subject about whether he/she is officially eligible or ineligible for the study.

Preexisting Condition: A preexisting condition is one that is present at the start of the study. A preexisting condition should be recorded as an AE if the frequency, intensity, or the character of the condition worsens during the study period.

- b. **Waitlist phase:** We will only capture AEs that are pertinent to the study. Specifically the following will be captured:

1. Patient death,
2. Patient develops a condition that would exclude them from the study,
3. Patient is de-listed (taken off the heart transplant waitlist),
4. Patient is made inactive on the transplant waitlist,
5. Patient is transplanted with a non-HCV heart.

In order to ascertain these events, we will review the patient's medical record once a month, and will contact the patient (by phone, e-mail, or in-person) every 6-8 weeks.

- c. **Post-transplant phase:** All AEs will be assessed at every clinic visit when the subject is seen by a member of the study team.

- d. **Post-study:** At the last scheduled visit, the investigator will instruct each subject to report any subsequent event(s) that the subject, or the subject's personal physician, believes might reasonably be related to participation in this study.

All unresolved AEs considered possibly, probably or definitely related to the study drug should be followed by the investigator until the events are resolved, the subject is lost to follow-up, or the AE is otherwise explained. The investigator should notify the IRB of any death or AE occurring at any time after a subject has discontinued or terminated study participation that may reasonably be related to this study. The IRB will also be notified if the investigator should become aware of the development of cancer or of a congenital anomaly in a subsequently conceived offspring of a subject that has participated in this study.

General Physical Examination Findings (screening, post-transplant, and post-study phases)

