12.7.4.1. Reporting Process

UPs posing risks to subjects or others as noted above will be reported to local IRB using a Medwatch or CIOMS report of the event (including a description of the event with information regarding its fulfillment of the above criteria, follow-up/resolution and need for revision to consent form and/or other study documentation) will be completed.

All Serious Adverse Events, regardless of causal relationship to the investigational product, will be forwarded to **Merck Worldwide Product Safety** via fax (**[contact]**) within 2 working days of the investigator becoming aware of the event and no later than 3 calendar days.

The Principal Investigator is expected to provide as much of the following information:

- Protocol name and number
- Subject identifiers (no PHI will be shared with the IRB, unless requested)
- Demographic data
- Nature of the event
- Severity of the event
- Probable relationship (causality) of AE to study procedure
- Date and time of AE onset
- Date and time of AE resolution, if available
- Concomitant medications that the participant was taking for an underlying medical condition or disease and the therapeutic agents used for the treatment of the adverse event
 - Clinical assessment of participant conducted at time of SAE/AE
 - Results of any laboratory and/or diagnostic procedures, and treatment
 - Follow-up plan
 - Outcome
 - Autopsy findings (if appropriate)

The Principal Investigator will provide details about the AE/ADE as they become available. If additional information cannot be obtained for whatever reason, this will be documented. The Principal Investigator should inform the IRB when no other information is expected. The Principal Investigator should provide the IRB with a logical, complete, and accurate narrative description of the SAE based upon the above information.

The Principal Investigator should promptly determine an assessment of causality

The IRB determines if any corrective actions should be initiated as a result of any known specific or collective SAE/AE(s) and inform the principal investigator of the corrective action (e.g., revision of informed consent form, protocol, CRF).

The Principal Investigator/designee should keep originals or photocopies of all relevant documentation, including facsimile confirmations, and file them in the participant's file.

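### The relatedness scale in 12.7.2 grades events against research procedures as a whole, so a rating made under it does not identify the drug-attributable events that the safety endpoint needs.

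*Combined protocol and SAP*

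**What the plan says.** Section 5.2 sets a "Primary safety objective: To determine the safety of administration of open-label Zepatier among HCV-negative patients" who receive an HCV-positive heart and become infected. The matching endpoint in the Synopsis is: "Determine if there are major adverse events attributable to HCV therapy in post-heart transplant patients". Section 9.2.1 names two sources of events. One is events "related both to receipt of a heart transplant from an HCV-positive donor among HCV-negative subjects with heart failure"; the other is given as "and adverse events related to administration of Zepatier".

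Causality is graded in 12.7.2 on five levels, from definite to unrelated. The definite level reads "the AE/ADE is clearly related to the research procedures", and the other four use the same reference. The list of items to supply in an event report (12.7.4.1) includes "Probable relationship (causality) of AE to study procedure".

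Section 12.7.3 contains a follow-up rule with a different reference: "All unresolved AEs considered possibly, probably or definitely related to the study drug should be followed by the investigator". Sections 10.3 and 10.6 say that the safety analysis will summarise how often toxicities occur and how severe they are. Neither mentions relatedness.

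**The concern.** The endpoint asks about one cause, the HCV drugs, while the scale asks about the research as a whole. In this trial that can include Zepatier, ribavirin or sofosbuvir where given, the HCV-positive heart with the infection it carries, and research blood draws. An investigator who follows 12.7.2 exactly can grade an event as probably related and leave no record of which of these was meant.

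The Synopsis lists no control. No comparison group can show which events would have occurred after transplantation and infection without the drug, so attribution case by case carries most of the weight of the drug-safety conclusion. If it is not recorded by cause when the event is assessed, the count of drug-attributable events rests on later reconstruction.

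**Working it through.** The plan states no figure on this point, so there is none to reproduce. The check sets the sections side by side.

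1. **What the endpoint needs.** The Synopsis needs attribution to HCV therapy. Section 9.2.1 needs Zepatier-related events and events related to the HCV-positive heart. Section 12.7.3 needs relatedness to the study drug.

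2. **What the scale supplies.** All 5 of the 5 levels in 12.7.2 refer to research procedures. The reporting item in 12.7.4.1 refers to study procedure. The expedited-reporting criterion in 12.7.4 again refers to research procedures.

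3. **Whether the term is divided anywhere.** It is not. The worked example in the 12.7.4 table takes an effect that went away once the drug was stopped and grades it possibly related. Drug effects are therefore meant to fall inside the general rating, alongside anything else the term covers.

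4. **Whether the drug-specific text closes the gap.**
   - 12.7.1 defines a suspected adverse reaction against the drug or investigational product. This is a yes-or-no definition, not a graded rating. The 12.7.4 table then explains the suspected fatal and life-threatening events in terms of relatedness to the research, which leads back to the general reference.
   - 12.6 relies on a judgement that an event is drug-related, without saying how it is graded or recorded.
   - 12.7.3 borrows the possible, probable and definite levels for the study drug, but 12.7.2 defines those levels against something else.

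   Together these show intent. None defines a graded drug rating or requires one to be recorded.

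5. **Whether the analysis repairs it.** Sections 10.3 and 10.6 specify no tabulation by relatedness or by cause.

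6. **An illustration from the protocol's own risk text.** Section 12.5 reports late aminotransferase rises above 5 times the upper limit of normal in about 1-3% of patients in earlier Zepatier trials. Section 12.10.5 says that HCV itself can cause severe acute liver inflammation. Suppose that two investigators each see an on-treatment aminotransferase rise. One blames the drug and the other the infection, and both grade it probable. Under 12.7.2 the two records are identical, yet only the first belongs in the endpoint.

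7. **Leverage of one event.** The Abstract plans for 10 treated subjects. If one subject's only qualifying event is reassigned from infection to drug, the proportion with a drug-attributable event changes by 1/10 = 10 percentage points. This shows how sensitive the result is; it does not estimate how often reassignment would occur.

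**The case against.** The strongest reply is that the protocol, read as a whole, does tell investigators to judge drug causality. Section 12.7.1 defines it, 12.7.3 applies graded terms to it, 12.6 depends on it, and 9.2.1 treats Zepatier-related events as a class of their own. The AE form is named in 12.7.2 but its fields are not shown, so it may already have a drug-relatedness field. The list in 12.7.4.1 describes what goes into an event report and is not shown to be the data-capture form. The trial also collects medication data, pill counts and drug diaries, and HCV RNA and liver tests at most visits; event reports carry onset and resolution dates. All serious events go to the drug's manufacturer whatever their cause, and the DSMB evaluates them. With about 10 treated subjects, case-by-case review is feasible.

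Much of this stands. A reader might infer that the endpoint cannot be derived from the data collected, or that the follow-up rule in 12.7.3 has nothing to act on. The documents support neither: the form is not shown, later attribution is possible, and 12.7.3 itself calls for a drug judgement. Nor does the scale distort the planned summaries of incidence and grade, which do not use relatedness.

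The mismatch remains. The defined scale and the endpoint have different references, and no section requires the rating that the endpoint needs. Attribution reconstructed later, in an open-label trial without a control, is weaker than one made prospectively under a stated rule.

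**Conclusion.** The point holds as a mismatch between a stated rule and the endpoint it should serve. Ratings made under 12.7.2 alone do not identify events attributable to HCV therapy, and they do not separate Zepatier-related events from those related to the HCV-positive heart. It should be corrected, but it does not undermine the trial: the SVR-12 endpoint and the incidence and grade summaries are unaffected.

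The number of events affected cannot be estimated from the documents. It may be tempting to use the 30-day readmission figure of about 40% in 12.10.1. That figure covers readmissions after heart transplantation in general and says nothing about how the scale would classify them, and 12.7.3 excludes some hospitalisations from adverse event reporting.

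Two assumptions apply. The first is that the AE form follows 12.7.2. If it already records drug relatedness, the change only brings the protocol into line with the form. The second is that research procedures, which the protocol does not define, can be read to include the heart and the infection it transmits. If sites read the term more narrowly, ratings would differ by reading, which is also a reason to define it.

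**What to change.** - **12.7.2 and the AE form:** keep the five levels, but record them separately for (a) Zepatier, (b) ribavirin or sofosbuvir when given, (c) the HCV-positive heart or donor-derived HCV, and (d) other research procedures. Align the causality item in 12.7.4.1.
- **Endpoint:** define the Synopsis endpoint as major adverse events rated possible, probable or definite for (a) or (b). Report (c) alongside, which also serves 9.2.1.
- **10.6:** add a tabulation of events by cause, level of relatedness and grade.
- **12.6 and 12.7.3:** reconcile the drug-related and study-drug wording with these ratings, stating which rating each sentence refers to. The content of any rule on stopping study drug stays with the sponsor.

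Cost: protocol wording and a few form fields. If the form now holds a single rating, four ratings add 4 - 1 = 3 judgements per event, or 2 when neither ribavirin nor sofosbuvir is given. No new visits or tests are needed.
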